3.5.3. Final Analysis

The final analysis of the study will occur approximately 3 years after the last participant is enrolled.

At the time of final analysis, analyses performed during the primary analysis will be repeated using updated data objectives will be analyzed. Additional analyses for safety or efficacy endpoints may be performed if needed or if requested by authorities.

4. DATA HANDLING DEFINITIONS AND CONVENTIONS

4.1. Scheduled Study Evaluations and Study Periods

4.1.1. Start of Study

A participant is considered to have started the study and entered the screening period when they have signed the ICF.

4.1.2. Day 1

The reference start date is designated as Day 1.

The reference start date for all safety and efficacy assessments (eg, AE onset, laboratory abnormality occurrence, vital sign measurements, dose interruption) will be the earliest among start dates of study drug.

For any nonsafety screening assessments or events such as baseline disease characteristics or medical history (eg, time since diagnosis of disease) that occurred prior to the earliest start date of any study drug, the reference start date will be the earliest among start dates of study drugs.

4.1.3. Study Day

The study day describes the day of the event or assessment date, relative to the reference start date.

If a visit/reporting date is on or after Day 1, then the study day at the visit/reporting date will be calculated as

```
Day \# = (visit/reporting date - Day 1 date + 1).
```

If the visit/reporting date is before Day 1, then the study day at the visit/reporting date will be calculated as

```
Day \# = (visit/reporting date - Day 1 date).
```

A study day of -1 indicates 1 day before Day 1.

The study day will be displayed in the data listings.

4.1.4. Baseline Value

Baseline is the last nonmissing measurement obtained before the first administration of any study drug, unless otherwise defined.

Values from assessments specified to be performed after the first dose of any study drug (eg, vital sign assessments during and after the tafasitamab infusion) are not considered as baseline values.

When scheduled assessments and unscheduled assessments occur on the same day and the time of the assessment or time of first dose is not available, the following convention will be used to determine baseline:

- If both a scheduled and an unscheduled visit occur on the day of the first dose and the time is missing, the scheduled assessment will be used as baseline.
- If all scheduled assessments are missing on the day of the first dose and an unscheduled assessment is available, the unscheduled assessment will be used as baseline.

4.1.5. Reference End Date

The reference end date will be the date of the last administration of any study drug.

4.1.6. Date of Last Contact

The date of last contact will be derived as the latest date among the following:

- Actual assessment dates considering all assessments (laboratory sample collection, vital signs, ECOG performance status, B symptoms, ECG measurement, tumor imaging), including scheduled and unscheduled visits.
- Date of new antilymphoma treatment administered after study drug discontinuation.
- Adverse event end date. If the AE is ongoing, then the AE start date will be used.
- Date of last interaction with participant collected in the "End of Study/Early Follow-Up Discontinuation" eCRF.
- Date of death from the "Death" eCRF.
- Date of study completion or withdrawal from the "End of Study/Early Follow-Up Discontinuation" eCRF.
- Date of study treatment completion or discontinuation from the "End of Treatment/Early Discontinuation of Treatment" eCRF.

4.1.7. Analysis Visit Windows and eCRF Visit Windows

Unless otherwise specified, for parameters that will be summarized by visit, the nominal visit as recorded in the eCRF will be used. There will be no additional analysis windows based on the assessment date. In order to summarize over time, parameters recorded at each visit (eg, ECOG performance status, vital signs) and assessments (including unscheduled ones) will be time-slotted if indicated.

4.1.8. Unscheduled Visits

In this study, unscheduled visits, as recorded in the "Unscheduled Visit Date of Visit" eCRF, are timepoints not planned in the Protocol.

Unscheduled visits will be listed and ordered chronologically by date.

Unscheduled visits will be incorporated in the baseline calculation and overall postbaseline summary. If the date is incomplete but it can be determined that values were measured during the treatment phase, the unscheduled visit will be incorporated in the overall postbaseline summaries. Unscheduled visits will be excluded from the per timepoint/visit presentation.

4.1.9. Handling of Missing and Incomplete Dates

In general, values for missing dates will not be handled unless methods for handling missing dates are specified in this section or relevant sections. The original reported dates collected in the eCRF should be used in all relevant listings. The following rules will be used for handling partial dates for analyses requiring dates.

When the date of the last dose is used in deriving variables such as duration of treatment or TEAE flag, a missing or partial date of the last dose will be handled as follows:

- If only the day is missing, then the earlier date of the last day of the month or the date that the participant discontinued treatment will be used.
- If both the month and day are missing, then the earlier date of 31 DEC of the year or the date that the participant discontinued treatment will be used.
- Otherwise, the date that the participant discontinued treatment will be used as the date of the last dose.

For relevant efficacy endpoints, a partial date of the death date will be handled as follows in the calculation:

- If mmyyyy for the last known alive date = mmyyyy for the death date, then the death date will be set to the day after the last known alive date.
- If mmyyyy for the last known alive date < mmyyyy for the death date, then the death date will be set to the first day of the death month.
- Otherwise, the partial death date will not be imputed.

4.2. Study Drug Administration

4.2.1. Study Drug and Study Treatment

Study drug refers to the individual drug, tafasitamab or LEN. Study treatment refers to tafasitamab in combination with LEN.

4.2.2. Date of First Administration of Study Drugs

The date of first administration of a study drug ("start date of study drug") is the first date when a nonzero dose of a study drug is administered. Start date of study drug is defined for each drug that is part of the study treatment.

4.2.3. Date of Last Administration of Study Drugs

The date of last administration of study drug ("last date of study drug") is the last date when a nonzero dose of study drug is administered. Last date of study drug is defined for each drug that is part of the study treatment. For tafasitamab, this date defines the EOT.

4.2.4. Date of First Administration of Study Treatment

The date of first administration of study treatment ("start date of study treatment") is the first date when a nonzero dose of any component of the study treatment is administered. For example, if the first dose of tafasitamab is taken on 03 JAN 2022, and the first dose of LEN is taken on 05 JAN 2022, then the "start date of study treatment" is 03 JAN 2022. In case of exposure to only 1 component of the study treatment, the date of first administration of study drug will be used.

4.2.5. Date of Last Administration of Study Treatment

The date of last administration of study treatment ("last date of study treatment") is the last date when a nonzero dose of any component of the study treatment is administered. For example, if the last dose of tafasitamab is taken on 13 APR 2022, and last dose of LEN is taken on 20 APR 2022, then the "last date of study treatment" is 20 APR 2022. In case of exposure to only 1 component of the study treatment, the date of last administration of study drug will be used.

4.3. Other Definitions

4.3.1. Study Cohorts

Participants will receive tafasitamab in combination with LEN in 28-day cycles.

- •

4.3.2. Screen Failures

Screen failures are defined as participants who consent to participate in the clinical study but are not subsequently entered into the treatment period.

4.3.3. Time Units

A month-length is 30.4375 days (365.25 / 12). If duration is to be reported in months, the duration in days will be divided by 30.4375. If duration is to be reported in years, the duration in days will be divided by 365.25.

4.3.4. Change From Baseline Calculation

The absolute change from baseline will be calculated as

change from baseline = visit value – baseline value.

The percentage change from baseline will be calculated as

percentage change from baseline = $[(visit value - baseline value) / baseline value] \times 100.$

4.3.5. End of Study

The EOS is reached when all participants still receiving study treatment have been followed for at least 3 years, or when the last participant on study has completed their last visit, whichever occurs first.

5. STATISTICAL METHODOLOGY

5.1. General Methodology

Unless otherwise noted, SAS® software (SAS Institute Inc, Cary, NC; v9 or later) will be used for the generation of all tables, graphs, and statistical analyses. Descriptive summaries for continuous variables will include but not be limited to the number of observations, mean, standard deviation, median, minimum, and maximum. Descriptive summaries for categorical variables will include the number and percentage of participants in each category.

5.2. Treatment Groups

Data will be summarized overall and by treatment group

5.3. Analysis Sets

5.3.1. Screened Participants Set

The SPS will consist of all participants who signed the ICF and completed the "Informed Consent" eCRF. Participants who signed the ICF and fulfilled screening criteria but never started any study drug will be listed. Screen failures will not be included in any of the summary tables (except in the screened participants disposition table).

5.3.2. Analysis Set for the Primary Estimand: Primary Analysis Set

A detailed description of the primary estimand for this study can be found in Protocol Section 4.1.1.

The PAS will include all participants who receive at least 1 of the higher tafasitamab doses at either 24 or 30 mg/kg and who had at least 1 postbaseline safety assessment.

A valid safety assessment includes death.

5.3.3. Enrolled Participant Set

The ENR will consist of all participants who received at least 1 dose of study drug (tafasitamab OR LEN).

5.3.4. Full Analysis Set

The FAS will include all participants who received at least 1 dose of study treatment (tafasitamab AND LEN).

Participants will be analyzed according to the dose group to which they were initially assigned.

5.3.5. Safety Analysis Set

The SAF will include all participants who received at least 1 dose of study drug (tafasitamab or LEN) and had at least 1 postbaseline safety assessment. A valid safety assessment includes death. Treatment groups for this set will be determined according to the actual treatment the participant received regardless of assigned study treatment.

All safety analyses will be conducted using the SAF.

5.3.6. Per-Protocol Set

Participants included in FAS with at least 1 valid postbaseline assessment for ORR and without any important Protocol deviations that would confound efficacy analysis will be included in the PPS. There may be other conditions leading to exclusion from the PPS, such as ineligibility per central pathology assessment.

Sensitivity analyses for efficacy endpoints may be performed using the PPS.

5.3.8. Pharmacokinetic Analysis Set

The PKAS will include all participants who received at least 1 dose of tafasitamab and have at least 1 quantifiable serum tafasitamab concentration.

5.3.9. Immunogenicity Analysis Set

The IAS will include all participants who received at least 1 dose of tafasitamab and have at least 1 valid anti-tafasitamab antibody assessment.

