**Table 1: Objectives and Corresponding Endpoints**

Objectives	Endpoints
Primary	

 
To evaluate the safety and tolerability of tafasitamab administered ██████████ in combination with lenalidomide in R/R DLBCL patients
 
To determine a recommended dose for tafasitamab ██████████ administration in combination with lenalidomide in R/R DLBCL patients
 
	Incidence and severity of TEAEs
Secondary	
To evaluate the pharmacokinetic profile of tafasitamab after ██████████ dosing in combination with lenalidomide	Tafasitamab serum concentrations after 3 ( $C_{trough}$ and $C_{max}$ ) and 12 ( $C_{trough}$ ) treatment cycles
To assess anti-tumor activity of tafasitamab after ██████████ dosing in combination with lenalidomide	
 
Best Objective Response Rate (ORR) by investigator assessment up to treatment Cycle 12 based on Cheson et al. (2007)
 
Duration of Response (DoR) by investigator assessment based on Cheson et al. (2007)
 
Progression-Free Survival by investigator assessment based on Cheson et al. (2007)
 

To assess the incidence of anti-drug antibodies to tafasitamab	Number and percentage of patients developing anti-tafasitamab antibodies up to treatment Cycle 12

Abbreviations:  $C_{max}$ =maximum concentration;  $C_{trough}$ =minimum concentration; DLBCL=diffuse large B-cell lymphoma; ██████████; R/R=relapsed/refractory; TEAEs=treatment-emergent adverse events. Each treatment cycle is 28 days.

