### 10.2.6 Immunogenicity Analysis Set (IAS)

The IAS includes all patients who have at least one valid anti-tafasitamab antibody assessment.

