5.3.10. Reason of Exclusion From Analysis Sets

Participants may be excluded from the analysis sets for the reasons presented in Table 2.

Table 2: Reasons for Exclusion From Analysis Sets

Analysis Set	Reason for Exclusion From Analysis Set
SPS	Not applicable
PAS	 No tafasitamab dose of No postbaseline safety assessment
ENR	No dose of any study drug
FAS	No dose of any component of study treatment
SAF	 No dose of any study drug No postbaseline safety assessment
PPS	 No dose of any component of study treatment Central pathology diagnosis different from investigator diagnosis No postbaseline ORR assessment Important Protocol deviations or other conditions that influence efficacy
PKAS	 No dose of tafasitamab No quantifiable serum tafasitamab concentration
IAS	No dose of tafasitamab No anti-tafasitamab antibody assessment

Note: If a participant has more than 1 reason for exclusion from any analysis set, then only the highest-ranking reason will be considered. For example, for the PPS, if a participant is excluded because of "no dose of any component of study treatment" and "no postbaseline response assessment," then only "no dose of any component of study treatment" will be counted when summarizing the reasons for exclusion from the PPS.

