9.2. Immunogenicity Analysis

Serum samples for the assessment of anti-tafasitamab antibodies will be collected as per the schedule of assessments detailed in Section 2 of the Protocol. In order to determine a participant's anti-tafasitamab antibody status, as a first step, a screening assay will be performed. Then, all screened positive samples will be tested again in a confirmatory assay. For all confirmed positive samples, the following additional assays will be performed: a semiquantitative ADA titer will be determined, the specificity toward MOR00208-hIgG1 or MOR00208-hIgG1/2a will be determined, and an nAb will be performed.

Anti-tafasitamab antibody samples will be defined as negative if they are screened or confirmed negative. Anti-tafasitamab antibody samples will be defined as positive if they are positive in

both the screening and the confirmatory assays. For all positive samples, an anti-tafasitamab antibody titer will be determined.

The immunogenicity data will be summarized for each treatment group and/or cohort and overall, using the IAS, as follows:

- Summary of the anti-tafasitamab antibody status; the number and percentage of participants will be tabulated to present the following categories:
 - Participants with pre-existing anti-tafasitamab antibodies (ie, participants who are positive for anti-tafasitamab antibodies on Cycle 1 Day 1).
 - Participants without anti-tafasitamab antibodies after treatment initiation (ie, participants who are negative for anti-tafasitamab antibodies on all occasions after Cycle 1 Day 1, irrespective of the baseline result).
 - Participants with anti-tafasitamab antibodies after treatment initiation (ie, participants who are positive for anti-tafasitamab antibodies on any occasion after Cycle 1 Day 1).
 - Participants with treatment-induced anti-tafasitamab antibodies (ie, participants who are negative for anti-tafasitamab antibodies on Cycle 1 Day 1 and positive on any other occasion).
 - Participants with treatment-boosted anti-tafasitamab antibodies (ie, participants who are positive for anti-tafasitamab antibodies on Cycle 1 Day 1 and who developed an increased titer on any other occasion).
- Summary of anti-tafasitamab antibody response per visit; the following will be tabulated:
 - Total number of participants
 - Number and percentage positive
 - Number and percentage negative
 - Number and percentage missing
- Summary of anti-tafasitamab antibody titer per visit; the following will be tabulated:

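### The immunogenicity set admits participants with only a pre-dose antibody sample, so the percentage developing anti-tafasitamab antibodies can be understated

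*SAP*

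**What the plan says.** The endpoint in Protocol Table 1 is "Number and percentage of patients developing anti-tafasitamab antibodies up to treatment Cycle 12".

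The SAP (section 5.3.9) defines the IAS as participants with "at least 1 dose of tafasitamab and have at least 1 valid anti-tafasitamab antibody assessment". Protocol section 10.2.6 is looser and has no dosing condition: "The IAS includes all patients who have at least one valid anti-tafasitamab antibody assessment". The only grounds for exclusion in SAP Table 2 (section 5.3.10) are "No dose of tafasitamab No anti-tafasitamab antibody assessment". None of the three asks for a result obtained after dosing.

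SAP section 9.2 names one set for all the ADA tables: "The immunogenicity data will be summarized for each treatment group and/or cohort and overall, using the IAS, as follows". Two of its categories matter here. Treatment-induced ADA covers "participants who are negative for anti-tafasitamab antibodies on Cycle 1 Day 1 and positive on any other occasion". The category without antibodies after treatment initiation covers "participants who are negative for anti-tafasitamab antibodies on all occasions after Cycle 1 Day 1, irrespective of the baseline result".

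In the Schedule of Assessments (Protocol section 2), the Cycle 1 Day 1 ADA sample is marked as taken before study treatment. The next scheduled samples are on Day 1 of Cycles 2 and 3, also pre-dose for that day. Sampling continues to Cycle 12, with a further sample at the end-of-treatment (EOT) visit unless the patient was treated beyond Cycle 12.

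**The concern.** Developing antibodies is a change after exposure, so observing it needs at least one sample after exposure. The IAS does not require one. For a participant whose only valid result is the baseline one, absence of data can be reported as a negative finding, and the participant adds to the denominator with no chance of adding to the numerator. Any such dilution can only lower the reported percentage, which is the favourable direction for an immunogenicity endpoint.

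The SAP takes more care elsewhere. The Primary Analysis Set and the Safety Analysis Set each need a postbaseline safety assessment, and the Per-Protocol Set needs a valid postbaseline response assessment. In the ORR analysis, participants without an adequate assessment count as nonresponders and are tabulated by reason. The participant-level ADA status table has no not-evaluable category.

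What is at stake is the accuracy of one descriptive secondary percentage. No hypothesis test or stated decision rule depends on it.

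**Working it through.** **1. Is there a figure to reproduce?** No. The documents give no expected ADA incidence, precision target or sample-size argument for immunogenicity. The question is what the rule does to the denominator.

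**2. How the rule classifies a dosed participant whose only valid ADA result is from Cycle 1 Day 1**

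| SAP 9.2 category | Outcome |
|---|---|
| In the IAS | Yes: one dose, one valid result |
| Pre-existing ADA | Yes if the baseline result is positive |
| Without ADA after treatment initiation | Condition met by default: there is no later occasion to contradict it |
| With ADA after treatment initiation | Cannot be met |
| Treatment-induced | Cannot be met |
| Treatment-boosted | Cannot be met |

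**3. Who would be in this position?** A patient who stops during Cycle 1 is still due an EOT visit within 14 days of the decision to stop (Protocol section 8.2), and that visit includes an ADA sample. Those left are mainly patients who die, withdraw or are lost before both Cycle 2 Day 1 and the EOT sample. Protocol section 8.4 lets patients who leave for non-safety reasons within 35 days be replaced. Cycle 2 Day 1 is nominally Day 29, and no rule removes a replaced but dosed patient from the IAS.

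**4. Inputs**
- N = 51: approximate planned enrolment (Protocol synopsis), assuming all enter the IAS.
- k = participants with no valid post-dose ADA result. Not in the documents; assumed 0 to 5. The upper end borrows from L-MIND, where 8 of 80 patients (10.0%) had no valid post-baseline scan (Protocol section 3.3.2): 0.10 × 51 = 5.1. That is an imaging figure and only a rough proxy.
- x = participants with treatment-induced ADA. Not in the documents; 0, 1, 5 and 10 are illustrative.
- Everyone is assumed to have a valid baseline result.

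**5. Formulas**
- As written: x/N.
- With a post-dose requirement: x/(N − k).
- Relative understatement for x > 0: 1 − (x/N) ÷ (x/(N − k)) = k/N.

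**6. Results**

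| x | As written, x/51 | k = 1, x/50 | k = 5, x/46 |
|---|---|---|---|
| 0 | 0% | 0% | 0% |
| 1 | 1.96% | 2.00% | 2.17% |
| 5 | 9.80% | 10.00% | 10.87% |
| 10 | 19.61% | 20.00% | 21.74% |

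The relative understatement is 0 for k = 0, 1/51 = 2.0% for k = 1, and 5/51 = 9.8% for k = 5. (That the last value equals the incidence for x = 5 is a coincidence.) With k = 5, the absolute gap is 10.87 − 9.80 = 1.07 points for x = 5 and 21.74 − 19.61 = 2.13 points for x = 10.

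If x = 0 the percentage does not move. Only the upper limit of an exact 95% interval would, from 7.0% (0/51) to 7.7% (0/46). The SAP does not plan an interval for ADA, so this is illustrative. The same Clopper-Pearson code reproduces the L-MIND response rate in Protocol section 3.3.2: 46/80 = 57.5%, interval 45.9% to 68.5%.

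**The case against.** The strongest reply is that the affected group is small and perhaps empty. The EOT sample should catch most early discontinuers. That stands: it limits k, but does not take the baseline-only participant out of the denominator.

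A second reply is that the SAP never states the percentage denominator in words, and that Protocol section 10.3 says missing values are treated as missing. On that view, nobody would be forced to count an unsampled participant as negative. This has some force, but the IAS is the only set named for these tables, and the general rule against substituting values does not remove anyone from an analysis set. Missing results are counted per visit and listed with reasons, so they are visible, but the participant-level percentage is not corrected.

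A third reply is that little depends on the result: the count of cases is unaffected and all analyses are exploratory. That is right, and it sets the weight of the point.

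Two stronger readings are tempting. A reader might infer that the ADA incidence is in fact understated. The documents do not show this, because it needs at least one baseline-only participant and at least one post-dose positive, and neither number is given. A reader might also infer that baseline-only participants can never count as ADA-positive. They can, as pre-existing positives; what they cannot be shown to have is treatment-induced or treatment-boosted ADA.

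**Conclusion.** The rule is wrong as written for an endpoint that needs a post-dose observation, but the consequence is conditional and small. The percentage developing ADA can be understated by a relative k/N. With k assumed between 0 and 5 of 51, that is 0 to 9.8%, or up to about 1.1 percentage points with five or fewer ADA cases and 2.1 points with ten. Any dilution from this source goes downward. There is none if every dosed participant has a post-dose result, and the percentage is unchanged if nobody is positive. The sizes rest on the assumed k, on all 51 entering the IAS, and on complete baseline results. This is a minor correction and does not threaten the trial's conclusions.

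**What to change.** In SAP section 9.2, state a denominator for each category:

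- **Pre-existing ADA:** keep the IAS.
- **With, and without, antibodies after treatment initiation:** IAS participants with at least one valid post-dose ADA result. Do not also require a baseline result here. These categories do not depend on one, and requiring it would drop a participant with a missing baseline and a genuine post-dose positive.
- **Treatment-induced and treatment-boosted:** as above, and also a valid baseline result.
- **Not evaluable:** add a row to the ADA status table counting IAS participants without a post-dose result.

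The IAS definitions in the SAP and Protocol can stay as they are. The cost is a few lines of SAP text and a change to one table, using data already collected. The downside is that the reported rate may become slightly less favourable.
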